2.8.4.2 Heart Failure (HF) Signs and Symptoms

The number and percentage of patients in the following heart failure signs and symptoms categories will be summarized by visit, treatment group and open-label sacubitril/valsartan:

- Paroxysmal nocturnal dyspnea (Absent, Present)
- Fatigue (Absent, Present)
- Edema (Absent, Trace, Feet and Ankles, Lower Legs or Thighs, Sacrum)
- Peripheral edema (Absent, Present)
- Dyspnea at rest (Absent, Present)

- Dyspnea at upon effort (Absent, Present)
- Orthopnea (Absent, Present)
- Rales (Absent, Basilar only, >1/3 of lung filled)
- Jugular venous distention (Absent, Present)
- Presence of a third heart sound (Absent, Present)
- NYHA classification (Class I, Class II, Class III, Class IV)

2.8.4.3 Angioedema

Data collected from the angioedema assessment and questionnaire will be summarized. Separate summaries will be produced for all angioedema and positively adjudicated angioedema. The number and percentage of patients for categorical variables and summary statistics for continuous variables for the following angioedema assessment data will be presented by study phase (see Section 2.1.1 for study phase definitions).

- Outcome (Not recovered/Not resolved, Recovered/Resolved, Recovering/Resolving, Recovered/Resolved with Sequelae, Fatal, Unknown)
 - Duration of angioedema in days [*end date – start date + 1*]
- Timing of event (After first dose, after multiple doses, dose not given) [not asked for events that occurred during Screening study phase]
 - Study medication discontinued due to event (No, Yes, Unknown)
 - Event occurred within 1 day of dosing (Within 1 day of dose but less than or equal to 1 hour, within 1 day of dose but greater than 1 hour, After 1 day of dosing, Unknown)
- History of prior angioedema or angioedema like event (No, Yes, Unknown)
 - If yes, medications taken at time of previous event:
 - ACE inhibitor
 - ARB
 - Renin inhibitor
 - Other medications
- Presence of hereditary angioedema (No, Yes, Unknown)
- Any family members with history of angioedema-like events (No, Yes, Unknown)
- Signs and symptoms for current event (No, Yes, Unknown)
 - Shortness of breath/dyspnea
 - Difficulty swallowing/dysphagia
 - Difficulty speaking/dysarthria

- Pain on swallowing/odynophagia
 - Stridor
 - Abdominal pain
 - Other
- Edema present (No, Yes)
 - Periorbital edema
 - Head edema
 - Neck edema
 - Lip edema
 - Tongue edema
 - Throat edema
 - Submandibular edema
 - Genitalia edema
 - Extremities edema
 - Other
- Previous edematous episodes (No, Yes, Unknown)
 - Number of previous edematous episodes
- ACEi taken in the past (before screening) (No, Yes, Unknown)
- ACEi taken (other than study medication) during trial participation after screening (No, Yes, Unknown)
 - Dose changed within 2 days of event (No, Yes, Unknown)
- ARB taken in the past (before screening) (No, Yes, Unknown)
- ARB taken (other than study medication) during trial participation after screening (No, Yes, Unknown)
 - Dose changed within 2 days of event (No, Yes, Unknown)
- Patient suffering from influenza, common cold or upper respiratory tract infection? (No, Yes, Unknown)
- Medication allergies (No, Yes, Unknown)
- Food allergies (No, Yes, Unknown)
- Potential causes of angioedema-like event (No, Yes, Unknown)
 - Food
 - Insect bite

- Animal exposure
- Medication
- Dental work
- Pollen
- Dust
- Concomitant disease
- Idiopathic
- Other
- Medical intervention (No, Yes)
 - Administration of H-1 blocker
 - Administration of H-2 blocker
 - Administration of steroids
 - Administration of epinephrine
 - Admission to hospital
 - Admission to ER
 - Endotracheal intubation
 - Tracheostomy
 - Discontinuation of ACE inhibitor (other than study medication)
 - Discontinuation of ARB (other than study medication)
 - Other

[figure not shown]
All angioedema assessment data will be listed. Additionally, the adjudicated assessment of the event will be listed separately.

2.9 Pharmacokinetic endpoints

Not applicable.

2.10 PD and PK/PD analyses

Not applicable.

2.12 Biomarkers

Biomarkers related to heart failure or mechanism of action (NT-proBNP, BNP, [REDACTED]) and spot urine samples for urinary biomarkers (UcGMP andUcGMP to Urinary Creatinine ratio) will be collected. Values and the change from baseline for each biomarker will be summarized by visit, treatment group and open-label sacubitril/valsartan. Analyses will be based on the FAS.

[figure not shown]
These and other selected biomarkers to be studied will be those believed to be relevant to the pathophysiology of heart failure, including those related to cardio-renal or vascular function, injury and/or fibrosis/remodeling. Biomarkers may include ones assessing cardio-renal or vascular benefit or ones related to the study drug mechanism of action. The list of blood and/or urine biomarkers may change during the course of the study as new or more relevant biomarkers are determined. Biomarker analysis may also occur retrospectively after study close with biomarker decisions dependent on study outcome and/or new biomarkers relevant to this heart failure patient population.

[figure not shown]
Biomarker values will be based on clinical laboratory samples processed and assessed by the central laboratory. Values below the limit of detection (LOD) (i.e., indicated as <LOD) will be converted to (0.5)(LOD) for purposes of analysis. Values indicated as 'Reported and Unreliable' will be excluded from analysis.

[figure not shown]
Biomarker samples from patients who withdrew consent will not be analyzed by the central laboratory.

BNP samples, which were originally assayed using P100 tubes, will be re-assayed using EDTA tubes for purposes of a side-by-side comparison of results where the value and change from baseline at each visit will be summarized for the subset of patients who have change from baseline values for the two BNP assays at the given visit.

Additional analysis of biomarkers is discussed in Sections 2.7 and 2.13.

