### Open-label extension epoch

The purpose of this open-label period is to observe the additional vascular effects of sacubitril/valsartan that occur beyond 12 weeks of treatment.

After 12 weeks of successful double-blind, active treatment, patients will continue into the 12 week open-label extension epoch. Patients will have received the final dose of double-blind treatment medication in the clinic at Week 12 (Visit 6).

- ALL patients will need to have a 36-hour washout from study treatment prior to starting the open-label extension to ensure that the blinding of the core study is maintained and to reduce the risk of angioedema.
- To facilitate this washout, patients will be instructed NOT to start their open-label treatment until the evening of the following day.
- All patients will start open-label treatment on sacubitril/valsartan 49/51 mg BID (Dose level 2), unless they completed the double-blind treatment epoch on Dose Level 1. Instead, these patients will enter the open-label epoch on sacubitril/valsartan 24/26 mg BID dose (Dose level 1).
- Study treatment will be force-titrated every 2 weeks to reach the target dose of sacubitril/valsartan 97/103 mg BID (Dose Level 3).

Deviation from the titration schedule or dose adjustments will only be allowed if indicated per protocol defined safety and tolerability criteria (See [Section 5.5.5](#), [Table 5-7](#)), and investigator judgement, if the investigator believes that adjustment/elimination of concomitant medications is not possible or does not alleviate the side effects of concern.

Follow-up safety visits will occur throughout the study at Weeks 1, 2, 4, 12, 14 and 24 (Visits 3, 4, 5, 6, 7, and 8).

Primary efficacy assessments will be conducted at Screening/Baseline, Day 1 (Visit 2) pre-randomization, and Week 12 (Visit 6).

[figure not shown]
Patients will be contacted by phone at approximately 30 days following the last administration of study treatment at Week 24 (Visit 8), or early withdrawal, in order to determine if any SAE(s) occurred during this time period. These SAEs will be recorded in the source document only and must be reported to Novartis. Attempts to contact the patient should also be recorded in the source document.

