**Figure 3-1 Study design**

### 3.2 Rationale for study design

The Evaluate-HF study is designed to provide a definitive assessment of the hemodynamic mechanism of action of sacubitril/valsartan in HFrEF.

In the CHOIR study, ACE/NEP inhibition with omapatrilat was associated with greater reductions in pulse pressure and Zc than enalapril after 12 weeks of treatment. Based on this, the double-blind treatment epoch of this study was designed to be 12 weeks. Additionally, given the superior results obtained with sacubitril/valsartan in the PARADIGM-HF trial, the duration of the double-blind period also limits the patients' exposure to the current standard of care, enalapril.

Prior to the double-blind treatment epoch, we wanted to ensure that patients had the opportunity to be optimized on treatment with guideline-directed therapy for HFrEF, other than ACEi and ARBs. As many patients are able to be up-titrated on medications in a 4 to 6 week period, we have allowed up to 6 weeks for the screening epoch.

We wanted the ability to assess the vascular effects of patients who switch from enalapril to sacubitril/valsartan as well as to understand if there are additional vascular effects in patients who have extended treatment with sacubitril/valsartan. We believe that 12 weeks of open-label treatment was enough time to evaluate both of these measures.

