#### **3.6.1 Risks**

Experience in the PARADIGM-HF trial, both in the run-in period as well as the double-blind randomization period, indicated that the major risks associated with the treatment of sacubitril/valsartan are renal dysfunction, [426 (10.14%) in 4203 patients in the double-blind treatment period], hyperkalemia, [488 (11.61%) in 4203 patients in the double-blind treatment period], and hypotension [740 (17.61%) in 4203 patients in the double-blind treatment period].

In PARADIGM-HF, patients treated with enalapril experienced these events at a similar rate with the exception of hypotension; renal dysfunction, [487 (11.52%) in 4229 patients in the double-blind treatment period]; hyperkalemia, [592 (14%) in 4229 patients in the double-blind treatment period]; and hypotension, [506 (11.97%) in 4229 patients in the double-blind treatment period]. Results from the TITRATION study indicated that patients whom are ACE or ARB naïve are at an increased risk of experiencing these adverse events.

In this study, the risk of experiencing renal dysfunction, hyperkalemia, and hypotension are mitigated by appropriate up-titration of the drug every two weeks. The risks are further mitigated by appropriate inclusion and exclusion criteria. Patients entering into the study must have an SBP of at least 140 mmHg if not treated for hypertension or a SBP of >105 mmHg if

they are currently on treatment. Additionally, patients are excluded if they have an eGFR < 30 ml/min/1.73 m^2 or a potassium > 5.2 mEq/L at screening.

Drug to drug interactions are known to occur with concomitant use of ACE/ARB/NEP and renin inhibitors. See [Section 5.5.8](#) for prohibited medications. Patient will be provided with study treatment instructions and their medication histories will be reviewed at Screening and all subsequent visits.

Sacubitril/valsartan, [19 (0.5%) in 4203 patients in the double-blind treatment period of PARADIGM-HF] and enalapril 10 (0.2%) in 4229 patients in the double-blind treatment period of PARADIGM-HF] may also cause angioedema. The risk of developing angioedema is increased if patients take both an ACEi and sacubitril/valsartan. To decrease this risk, patients will be required to undergo a 36-hour washout prior to randomization as well as the open-label treatment epoch to minimize the interaction between an ACEi and sacubitril/valsartan in potentiating the development of angioedema.

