2.1.1 General definitions

Study treatment

Patients will receive either sacubitril/valsartan or enalapril during the first 12 weeks of the study. Study treatment will refer to either of these two drugs.

Baseline

In general, baseline is defined as the last non-missing assessment prior to or on the start date of study treatment (randomization date for patients not treated). For hemodynamic variables baseline is defined as the assessment with a planned time point value of 'Visit_1_Baseline'.

Unscheduled assessments will be excluded from the determination of baseline.

Date of first administration of study treatment

Double-blind phase: The date of first administration of study treatment in the double-blind phase is defined as the first date a dose of study treatment is administered and recorded on the Dosage Administration Record - At Visit (Visit 2) electronic case report form (eCRF).

Open-label phase: The date of first administration of study treatment in the open-label phase is defined as the first date a dose of sacubitril/valsartan is administered in the open-label phase and recorded on the Dosage Administration Record - At Visit (Visit 7) eCRF.

Date of last administration of study treatment

Double-blind phase: The date of last administration of study treatment in the double-blind phase is defined as the last date a dose of study treatment is administered in the double-blind phase and recorded on the Dosage Administration Record - At Visit (Visit 6) eCRF. In the event this date is not available from the Dosage Administration Record - At Visit (Visit 6) eCRF, it will

be determined from the End of Study Treatment eCRF or Dosage Administration Record - Summary eCRF.

Open-label phase: The date of last administration of study treatment in the open-label phase is defined as the last date a dose of sacubitril/valsartan is administered in the open-label phase and recorded on the Dosage Administration Record - Summary eCRF.

The date of last administration of study treatment during the study is defined as the last date a dose of study treatment is administered and recorded on the End of Study Treatment eCRF. In the event this date is not available from the End of Study Treatment eCRF, it will be obtained from the Dosage Administration Record - Summary eCRF.

Study day

The study day describes the day of the assessment relative to the date of randomization.

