2.3.3 Demographics and other baseline characteristics

Demographics, baseline characteristics and disease history are collected at the screening visit. Descriptive summaries and/or listings will be provided. The number and percentage (categorical variables) and descriptive statistics (continuous data) for the information below will be summarized by treatment group and open-label sacubitril/valsartan.

The FAS will be used.

Demographics and baseline characteristics

Demographic variables include:

- Age (years), age group (<65, ≥65 years; and <75, ≥75 years)
- Sex (Male, Female)
 - Child bearing status (Able to bear children, Post-menopausal, Sterile)
- Race (Caucasian, Black, Asian, Native American, Pacific Islander, Other, Unknown)
- Ethnicity (Hispanic or Latino, Not Hispanic or Latino, Unknown)

General baseline characteristic variables include:

- Height (cm)
- Weight (kg)
- Body mass index (BMI) (kg/ m²) [*weight (kg)/height (m²)*]
 - BMI categories (<20, 20 - <25, 25 - 30, >30 kg/m²)
- Smoking history (Never, Current, Former)
- eGFR (ml/min/1.73 m²)

- eGFR categories (<45, 45 - <60, ≥60 ml/min/1.73 m²)
- Plasma NT-proBNP (pg/mL)
 - Plasma NT-proBNP categories (<450, 450 - <900, 900 - <1600, 1600 - <3200, ≥3200 pg/mL)
- PlasmaBNP (pg/mL)
 - Plasma BNP categories (<100, 100 - <225, 225 - <400, 400 - <800, ≥800 pg/mL)

Key hemodynamic baseline characteristic variables include:

- Aortic characteristic impedance (dyne x sec/cm⁵)
- Central (aortic) pulse pressure (mmHg)
- Carotid-femoral pulse wave velocity (m/sec), both untransformed values and negative inverse transformed values (niCFPWV = -1000/CFPWV)
- Augmentation index (%)
- Aorta-carotid reflection coefficient
- Carotid pulsatility index
- Central systolic pressure (mmHg)
- Central diastolic pressure (mmHg)
- Heart rate (bpm)

Key echocardiographic baseline characteristic variables include:

- Global longitudinal strain (%)
- Left atrial volume index (mL/m²)
- Mitral annular E' velocity (cm/sec)
- Mitral E/E'
- LVEF (%)
- Ventricular-vascular coupling (Ea/Ees)
- Left ventricular end systolic volume index (LVESVi) (mL/m²)
- Left ventricular end diastolic volume index (LVEDVi) (mL/m²)

Disease history

Disease history variables, as collected on the Heart Failure History eCRF at screening, include:

- NYHA classification [best value during the past month prior to screening visit] (I, II, III, IV)
- Primary heart failure etiology (Ischemic, Non-ischemic)

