2.8.4 Other safety data

2.8.4.1 Vital signs

All vital signs (systolic and diastolic blood pressure [mmHg], pulse rate [beats per minute], respiration rate [breaths per minute], weight [kg], height [cm], and BMI [kg/m²]) will be descriptively summarized at each visit by treatment group and open-label sacubitril/valsartan. Change from baseline will also be presented.

A separate summary table will be presented with the number and percentage of patients having notable vital signs based on changes relative to baseline values (see Section 5.4 for a list of notable vital signs) by study phase (see Section 2.1.1 for study phase definitions). Unscheduled assessments will be considered.

The incidence of hypotension through Week 12 will be calculated by treatment group. The relative risk (sacubitril/valsartan vs. enalapril) and 95% confidence interval will be presented. Hypotension will be determined from the vital signs data as systolic blood pressure <90 mmHg. Unscheduled assessments will be considered.

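### The readable SAP summaries place both treatment sequences in one open-label category measured from the pre-treatment baseline, so those tables cannot separate the switch effect from the extended-treatment effect

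*SAP*

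**What the plan says.** **Purpose of the epoch.** The protocol's open-label subsection of 3.1 says "The purpose of this open-label period is to observe the additional vascular effects of" sacubitril/valsartan after Week 12. Protocol 3.2 splits this into two questions. The first concerns switchers: "We wanted the ability to assess the vascular effects of patients who switch from enalapril to sacubitril/valsartan". The second is whether there are "additional vascular effects in patients who have extended treatment with sacubitril/valsartan".

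**Layout of the summaries.** SAP 2.3.3 says baseline information "will be summarized by treatment group and open-label sacubitril/valsartan". SAP 2.8.4.1 says vital signs "will be descriptively summarized at each visit by treatment group and open-label sacubitril/valsartan". SAP 2.12 uses the same grouping for biomarkers: "Values and the change from baseline for each biomarker will be summarized by visit, treatment group and open-label sacubitril/valsartan". So do the dosing summaries (2.4.1), medications (2.4.2), by-visit laboratory values (2.8.3) and heart failure signs (2.8.4.2). No readable section divides open-label data by randomized arm.

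**Reference value.** SAP 2.1.1 says: "In general, baseline is defined as the last non-missing assessment prior to or on the start date of study treatment". Hemodynamic variables use the Visit 1 assessment. The readable text defines no Week 12 reference.

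**What is specified differently.** Adverse events, deaths, angioedema and notable laboratory and vital-sign values are tabulated by study phase, without stating the columns. The incidence tables for hyperkalemia, worsening renal function and hypotension are by treatment group and stop at Week 12. SAP sections 2.11 and 2.13 are blacked out, and 2.12 points to 2.13 for further biomarker analysis.

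**The concern.** After Week 12 everyone takes the same drug, but there are two sequences with different Week 12 states. A switcher's change from the pre-treatment baseline mixes 12 weeks of enalapril with the response to the new drug. A continuer's change mixes the double-blind response with anything gained later. One column averages the two.

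The sequences also differ at entry. Under the protocol's open-label rules, patients enter on Dose Level 2 unless they finished the double-blind epoch on Dose Level 1. A continuer who finished on Dose Level 3 therefore takes a lower dose than before, while a switcher has first exposure. Week 14 vital signs and chemistry in one column would average these.

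The transition from an ACE inhibitor also belongs to one sequence only. Protocol 3.6.1 notes: "The risk of developing angioedema is increased if patients take both an ACEi and sacubitril/valsartan". Everyone has the 36-hour washout, but only the enalapril arm is moving off an ACE inhibitor.

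At stake is whether the open-label summaries can answer the questions the epoch was added for. The primary and secondary Week 12 comparisons are not touched.

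**Working it through.** **1. Patients per sequence.** Protocol 9.8 plans 432 patients with 20% dropout: 432 × 0.80 = 345.6, which reproduces the approximately 346 in Table 5-3. With 1:1 allocation and equal dropout, 346 / 2 = 173 per sequence.

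**2. What a pooled change can identify.** Let *E* and *S* be the mean Week 12 changes from baseline in the enalapril and sacubitril/valsartan arms, *a* the further change after switching, and *b* the further change with extended treatment. With equal arms:

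- pooled Week 24 change from baseline = [(*E* + *a*) + (*S* + *b*)] / 2
- pooled Week 12 to Week 24 change = (*a* + *b*) / 2

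Both depend on *a* and *b* only through their sum. For illustration take *E* = 0 and *S* = -30, the size of difference used in Protocol 9.8:

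| Switch *a* / extension *b* | Pooled Week 24 change | Pooled Week 12–24 change | Week 24 change by arm (enalapril / sacubitril/valsartan) |
|---|---|---|---|
| -30 / 0 | -30 | -15 | -30 / -30 |
| -20 / -10 | -30 | -15 | -20 / -40 |
| -15 / -15 | -30 | -15 | -15 / -45 |
| 0 / -30 | -30 | -15 | 0 / -60 |

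The four rows are different answers to the questions in Protocol 3.2 and give the same pooled figures. The Week 24 by-arm column tells them apart. The 30 is borrowed only for scale; the algebra holds for any variable summarized this way.

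**3. The same check for NT-proBNP, which SAP 2.12 does cover.** Protocol 9.8 assumes Week 12 ratios to baseline of 0.95 (enalapril) and 0.7125 (sacubitril/valsartan). Check: ln(0.95 / 0.7125) = 0.288, as stated there. With switch ratio *a* and extension ratio *b*, the pooled geometric mean ratio at Week 24 is √(0.95*a* × 0.7125*b*):

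- *a* = 0.75, *b* = 1 (all switch): √(0.7125 × 0.7125) = 0.7125
- *a* = 1, *b* = 0.75 (all extension): √(0.95 × 0.5344) = 0.7125
- *a* = 1, *b* = 1 (neither): √(0.95 × 0.7125) = 0.82

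The pooled value does move when the switch has an effect, from 0.82 to 0.7125. It cannot say which sequence moved it.

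**4. Cost in precision.** Halving the denominator widens an interval by √2 = 1.41. For NT-proBNP at Week 24, assume the log-scale SD of 0.85 that Protocol 9.8 gives for Week 12, and vary it by ±25% because no Week 24 value is given. The 95% half-width per sequence is 1.96 × 0.85 / √173 = 0.127 (0.095 to 0.158), a factor of exp(0.127) = 1.14 (1.10 to 1.17). Pooled it is 1.96 × 0.85 / √346 = 0.090, a factor of 1.09. These assume every entrant has a Week 24 value.

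**The case against.** **The aims are vascular, and the relevant text may be blacked out.** This is the strongest reply and it stands. The quoted 2.12 sentence is about descriptive biomarker summaries. No readable section gives the Week 24 hemodynamic analysis, and SAP section 4 shows that analyses exist outside the readable text (it transforms pulse wave velocity before analysis). A reader might infer that the whole SAP cannot show the switch or extension effects. The documents do not support that, because redacted text cannot be counted as absent.

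**Pooling is an inference.** The SAP never says that the sequences are combined, and table details sit in a separate shells document. This stands in part. But 2.3.3 applies the layout to data collected at screening, where a third heading makes sense only as a column of open-label entrants beside the two arms. Table 5-3 likewise lists one open-label row.

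**Safety is largely unaffected.** The hyperkalemia, renal and hypotension incidence tables stop at Week 12, so they contain no open-label data and nothing in them is diluted. For adverse events and angioedema the columns are simply not stated, so dilution there cannot be asserted either.

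**Listings and randomized arm are available.** They are, so a later split is possible. A listing is not a pre-specified summary, however, and a split chosen after the data are seen carries less weight.

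**Conclusion.** The point holds for the readable laboratory, vital-sign, heart failure sign, dosing, medication and biomarker summaries. As specified, they name one open-label category, with change where it is reported taken only from the pre-treatment baseline. Such tables cannot separate the two effects in Protocol 3.2: every switch/extension pair with the same sum (or, for ratios, the same product) gives the same pooled result. This rests on reading the layout as a single open-label column, and the worked figures assume equal arms.

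Two further inferences would go too far. One is that the pooled NT-proBNP change is blind to the switch. It is not: under the plan's own ratios it would be about 0.82 if neither arm changed after Week 12, and 0.7125 if switchers improved to the sacubitril/valsartan level. The other is that the Week 24 hemodynamic analysis is missing or wrong, which the readable documents cannot show.

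This is a worthwhile, low-cost improvement to descriptive tables. It does not affect the primary or secondary Week 12 analyses.

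**What to change.** - In SAP 2.3.3, 2.4.1, 2.4.2, 2.8.3, 2.8.4.1, 2.8.4.2 and 2.12, replace the single open-label heading with two columns by randomized arm: enalapril to sacubitril/valsartan, and sacubitril/valsartan throughout. A total column may stay.
- In SAP 2.1.1, define a Week 12 reference as the scheduled pre-dose Visit 6 value. For laboratory values, vital signs and biomarkers, show change from it beside change from the pre-treatment baseline at Weeks 14 and 24, where measured (biomarkers are not scheduled at Week 14). For heart failure signs, show the Week 12 distribution beside the later visits.
- State that the open-label phase of the adverse event, angioedema and notable-value tables uses the same two columns.
- Confirm that the blacked-out sections present Week 24 hemodynamics by randomized arm with a Week 12 reference, or align them.

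Cost: SAP wording and table shells only, with no new data or visits. Tables become wider, and each column holds about 173 patients instead of about 346, with intervals about 1.4 times as wide.
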